1.4.4 Non-Index Lesions

Any other measurable and abnormal nodal or extranodal lesions not selected for quantitation as index lesions may be considered non-index lesions. In addition, non-measurable evidence of lymphoma such as abnormal, non-measurable nodal lesions, extranodal lesions with both diameters < 1.0 cm, bone lesions, leptomeningeal disease, ascites, pleural or pericardial effusions, lymphangitis of the skin or lung, abdominal masses that are not confirmed and followed by imaging techniques, cystic lesions, previously irradiated lesions, or lesions with artifacts may be considered as non-index disease.

If present at baseline, up to 6 non-index lesions should be recorded. Measurements are not required.

Non-index disease will be used as a general reference to further characterize regression or progression of lymphoma during assessments of the objective tumor response during treatment. These lesions should be followed as "present" or "absent".

1.4.5 Spleen and Liver

Qualitative assessments of the sizes of the spleen and liver will be performed. In addition, the presence or absence of splenic nodules will be recorded.

At baseline and follow-up timepoints, the spleen and liver size will be reported as normal, enlarged not due to lymphoma (no nodules present), enlarged due to lymphoma (≥ 1 nodule present), unequivocal increase not due to lymphoma (no nodules present), or unequivocal progression (≥ 1 nodule present). For subjects with splenomegaly or hepatomegaly at baseline or at the nadirs for assessments of spleen and liver, evaluations will consider only changes relative to the enlargement of the organ (i.e., the portion of the LVD that is ≥ 12 cm by imaging for the spleen and ≥ 18 cm in LVD for the liver) at baseline or nadir, not changes relative to the total splenic LVD.

By imaging, the spleen will be considered enlarged if it is > 12 cm in LVD [Bezerra 2005, Asghar 2011], with the LVD being obtained by multiplying the number of sections on which the spleen is visualized by the thickness of the sections (e.g., if the spleen is seen in 14 contiguous cross-sectional images with 0.5-cm thickness, the LVD is recorded as 7 cm). An increase in splenic enlargement by $\geq 50\%$ (minimum increase of 2 cm) from nadir and the presence of ≥ 1 splenic nodule is required for declaration of splenic progression.

Version 9, 18 Feb 2020

Subjects with a normal spleen LVD (i.e., a LVD of ≤ 0 cm by physical examination or ≤ 12 cm by imaging) at nadir will only be considered to have progressed if the spleen attains a LVD of > 14 cm by imaging and there is ≥ 1 splenic nodule.

By imaging, the liver will be considered enlarged if it is > 18 cm in LVD [Erturk 2006]. An increase in liver enlargement by $\geq 50\%$ (minimum increase of 2 cm) from nadir and the presence of ≥ 1 hepatic nodule is required for declaration of hepatic progression. Subjects with a normal liver LVD (i.e., a LVD of ≤ 18 cm by imaging) at nadir will only be considered to have progressed if the liver attains a LVD of > 20 cm by imaging and there is ≥ 1 hepatic nodule.

1.4.6 Bone Marrow

Bone marrow assessments will be based on morphologic evaluation of bone marrow biopsies. Immunohistochemistry may be used to assess response if the sample is indeterminate by morphology.

In a subject who has a baseline bone marrow biopsy showing bone marrow lymphoma or does not have a baseline bone marrow examination, declaration of an on-study CR requires bone marrow biopsy documentation of the absence of bone marrow lymphoma. In a subject who has a baseline bone marrow biopsy showing no evidence of lymphoma, declaration of an on-study CR does not require bone marrow examination as long as other criteria for CR are met. Of note, in subjects with an FDG-PET avid lymphoma, declaration of an on-study CR can be based on FDG-PET documentation of the absence of bone marrow involvement, even if a bone marrow biopsy is not performed or not available.

1.4.7 Lymph Node Biopsy

Lymph node biopsy is not required in the determination of subject eligibility.

During study participation, a subject with a more indolent type of disease (e.g., CLL/SLL, FL) who has a lymph node biopsy indicating transformation to an aggressive lymphoma will be considered to have PD even in the absence of other evidence of PD. If the subject has no earlier objective documentation of PD, the date of the lymph node biopsy will be considered the date of PD.

1.5 Definitions of Tumor Response and Progression

Responses will be categorized as complete response (CR), partial response (PR), stable disease (SD), or progressive disease (PD). In addition, a response category of nonevaluable (NE) is provided for situations in which there is inadequate information to otherwise categorize response status.

The best overall response will be determined. The best overall response is the best ontreatment response from baseline recorded from the start of treatment until PD/recurrence. The baseline measurement will be taken as a reference for determinations of response. The nadir measurement will be taken as a reference for PD; this measurement constitutes the smallest measurement recorded, including the baseline measurement if this is the smallest measurement. For FDG-avid tumors, metabolic criteria for response by PET-CT will take precedence over anatomic criteria for response by contrast CT when assessing CR.

Version 9, 18 Feb 2020

1.5.1 Complete Response

To satisfy criteria for CR, all of the following conditions must be attained:

- No evidence of new disease
- Regression of all index nodal lesions to normal size (\leq 1.5 cm in the LD for nodes that were considered large at baseline and \leq 1.0 cm in the LPD for nodes that were considered small at baseline) (see Section 1.4.2 for definitions of large and small nodes)
- Regression to normal of all nodal non-index disease
- Disappearance of all detectable extranodal index and non-index disease
- Normal spleen and liver size by imaging studies, no hepatic or splenic lymphoma nodules, and no new liver or spleen enlargement
- Morphologically negative bone marrow based on an adequate unilateral core biopsy (> 20 mm unilateral core); if the sample is indeterminate by morphology, it should be negative by immunohistochemistry
- If PET performed, no evidence of residual disease i.e., score of 1 (no uptake above background), 2 (uptake ≤ mediastinum), or 3 (uptake > mediastinum but ≤ liver) on the Deauville 5-point scale.
- Negative for bone marrow involvement by PET for a PET-avid tumor or by an adequate unilateral core biopsy (> 20 mm unilateral core); if the bone marrow biopsy is indeterminate by morphology, it should be negative by immunohistochemistry.

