1.5.2 Partial Response

To satisfy criteria for PR, all of the following conditions must be attained:

- No evidence of new disease
- $A \ge 50\%$ decrease from baseline in the SPD of the index nodal and extranodal lesions
- No increase from the nadir in the size of non-index disease
- No increase from the nadir in the size of the liver or spleen and no new liver or spleen enlargement
- If PET performed:
 - Typically FDG-avid lymphoma: if no baseline PET scan or if the PET scan was positive before therapy, the on-treatment PET is positive in ≥ 1 previously involved site—i.e., score of 4 (uptake moderately > liver) or score of 5 (uptake markedly > liver) on the Deauville 5-point scale but with reduced uptake compared with baseline. If baseline PET was performed and was negative, there is no new PET evidence of disease.
 - Variably FDG-avid lymphoma/FDG-avidity unknown: if no pretreatment PET scan or if the pretreatment PET scan was negative for lymphoma, CT criteria should be used in assessing the tumor during treatment. If the PET scan was positive before therapy, the on-treatment PET is positive in ≥ 1 previously involved site.

Version 9, 18 Feb 2020

• Persistence of bone marrow involvement in a subject who meets other criteria for CR based on the disappearance of all nodal and extranodal masses

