11. ASSESSMENT OF EFFICACY

Tumor response will be assessed in the Dose Escalation Stage and Expansion Stage using modified Lugano Response Criteria for NHL (Cheson 2014) and revised guidelines for the diagnosis and treatment of CLL (Hallek 2008, Cheson 2012) (see Appendix 2).

Pretreatment tumor assessments will be performed within 30 days of the first dose (bone marrow assessment may be performed within 2 months prior to first dose) and will include diagnostic CT scans (with intravenous contract) or PET/CT for subjects with lymphoma (CT only for subjects with CLL/SLL), bone marrow aspirate/biopsy, complete blood counts and physical examination. It is anticipated that in most cases the PET and CT scans will be conducted using a single instrument, i.e., as a PET/CT scan (CT scans should be performed using a contiguous reconstruction algorithm of ≤ 5 mm). However, MRI is an acceptable alternative method for assessing disease in subjects who cannot receive intravenous contrast with CT scans. In such subjects MRI and PET scans will have to be obtained separately. Baseline bone marrow biopsies/aspirates may be omitted if not deemed essential for response assessment or patient management.

During treatment, radiology studies will be performed for tumor assessments within 7 days prior to Day 1 of Cycles 3, 5, 7 and then every 3 months thereafter as indicated in Table 8: Schedule of Assessments (LAM-002A Continuous Monotherapy Administration), Table 9: Schedule of Assessments (LAM-002A Intermittent Monotherapy Administration), Table 10: Schedule of Assessments (LAM-002A/Rituximab Combination Therapy), and Table 11: Schedule of Assessments (LAM-002A/Atezolizumab Combination Therapy) in Section 8.7. until PD or use of alternative antineoplastic therapy. If necessary per applicable response criteria, a repeat bone marrow biopsy or aspirate will be required for subjects who have a Complete Response (CR) by imaging and physical examination. Subjects with CLL/SLL who achieve CR will require assessment of minimal residual disease (MRD) by flow cytometry of bone marrow and peripheral blood.

Protocol: LAM-002A-NHL-CLN01

Version 9, 18 Feb 2020

Section 12. PHARMACOKINETIC ASSESSMENTS

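### Appendix 2 lymphoma criteria: an unconditional core-biopsy bullet in the CR list contradicts 1.4.6, and some PET-negative complete responders are left with no response category

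*Combined protocol and SAP*

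**What the plan says.** All references are to the lymphoma part of Appendix 2 unless stated. The text is the replacement wording in the amendment log.

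- **1.5.1, header:** "To satisfy criteria for CR, all of the following conditions must be attained".
- **1.5.1, first marrow bullet:** "Morphologically negative bone marrow based on an adequate unilateral core biopsy (> 20 mm unilateral core", with immunohistochemistry if morphology is indeterminate. No exception is stated.
- **1.5.1, last bullet:** "Negative for bone marrow involvement by PET for a PET-avid tumor or by an adequate unilateral core biopsy", with the same core length and immunohistochemistry provision.
- **1.4.6, negative baseline biopsy:** "declaration of an on-study CR does not require bone marrow examination as long as other criteria for CR are met".
- **1.4.6, FDG-avid lymphoma:** "declaration of an on-study CR can be based on FDG-PET documentation of the absence of bone marrow involvement", even where no biopsy is available.
- **1.4.6, remaining subjects:** where baseline marrow was positive or was not examined, and PET does not clear it, a negative biopsy is still needed for CR.
- **1.5.2 (PR):** this is also an all-of list, and its last bullet is "Persistence of bone marrow involvement in a subject who meets other criteria for CR based on the disappearance of all nodal and extranodal masses". Its PET bullet, for typically FDG-avid lymphoma with a positive or no baseline PET, needs an on-treatment PET that is still positive in at least one previously involved site.
- **1.5.3 (SD):** if PET-CT was done, it must show a Deauville score of 4 or 5.

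**The concern.** The first marrow bullet in 1.5.1 makes the PET option in the last bullet of the same list useless, and it cancels both allowances in 1.4.6. A subject can therefore be in CR under 1.4.6 and not in CR under 1.5.1 on identical data.

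The PR list should catch such a subject, but it has its own fault. Under an all-of header, persistent marrow involvement becomes a condition of every PR. That would bar an ordinary partial responder with residual nodes and clean marrow.

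At stake are the CR rate and, for one group, the ORR. Under Section 14.3, responders are subjects with CR, CRi or PR, and non-evaluable subjects count as failures. The FL accrual boundaries in Section 14.1.2 are counts of objective responses, so a complete responder with no category is lost from the numerator.

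**Working it through.** No sample size or power figure depends on these definitions. The check is to apply the lists to one kind of subject: complete regression on imaging, index-lesion SPD at least halved, no new disease, **no on-study marrow biopsy**. Three factors vary: baseline marrow (negative, positive, not examined), FDG avidity, and on-treatment PET (not done, negative). That gives 3 × 2 × 2 = 12 combinations.

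Assumptions: FDG-avid subjects had a positive baseline PET or none; the others had a negative baseline PET or none, so CT criteria govern their PR.

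| Baseline marrow | FDG-avid | PET | CR by 1.4.6 | CR by 1.5.1 | PR, last bullet mandatory | PR, last bullet an alternative | 1.5.3 PET bullet met |
|---|---|---|---|---|---|---|---|
| Negative | no | not done | yes | no | no | yes | yes |
| Negative | no | negative | yes | no | no | yes | no |
| Negative | yes | not done | yes | no | no | yes | yes |
| Negative | yes | negative | yes | no | no | **no** | **no** |
| Positive | no | not done | no | no | no | yes | yes |
| Positive | no | negative | no | no | no | yes | no |
| Positive | yes | not done | no | no | no | yes | yes |
| Positive | yes | negative | yes | no | no | **no** | **no** |
| Not examined | no | not done | no | no | no | yes | yes |
| Not examined | no | negative | no | no | no | yes | no |
| Not examined | yes | not done | no | no | no | yes | yes |
| Not examined | yes | negative | yes | no | no | **no** | **no** |

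1. Section 1.4.6 allows CR in 6 of 12 combinations; 1.5.1 allows it in none.
2. With the last PR bullet mandatory, none of the 12 is PR. With it as an alternative, 9 of 12 are PR.
3. On the alternative reading, the 6 combinations that 1.4.6 would call CR split evenly. Three become PR, so the CR rate changes and ORR does not. Three, all FDG-avid and PET-negative, fail CR on the biopsy bullet, PR because PET must be positive, and SD because the score must be 4 or 5.
4. In the other 6 combinations 1.4.6 also withholds CR, so there is no conflict about CR; they are PR on the alternative reading.

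These are kinds of subject, not frequencies. The documents give no basis for estimating how many subjects fall in each.

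**Size per subject.** 1/6 = 16.7 percentage points; 1/20 = 5 percentage points.

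**Effect on the FL boundaries at N = 20.** The exact one-sided 95% lower bound for x responders out of n is the 5th percentile of Beta(x, n − x + 1).

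- Monotherapy, plan's boundary 8/20: Beta(8, 13) gives 21.7%, which reproduces the plan's statement that 20% is met. With one responder lost, 7/20: Beta(7, 14) gives 17.7%, below 20%.
- Rituximab combination, plan's boundary 12/20: Beta(12, 9) gives 39.4%, which reproduces the plan's 39%. With one lost, 11/20: Beta(11, 10) gives 34.7%, below 39%.

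**The case against.** **The intent is clear.** Section 1.4.6 is the dedicated marrow rule. It agrees with the last bullet of 1.5.1, and the first marrow bullet looks like a leftover. This is fair as to intent. But 1.5.1 is the list that defines CR, and nothing says that 1.4.6 overrides it. The precedence given to PET in 1.5 is over anatomic criteria on contrast CT, not over a marrow biopsy.

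**The PR bullet is a drafting slip.** It probably is. It follows a page break with a different list marker, and the mandatory reading would bar ordinary partial responders. A reader might infer that every complete responder without a biopsy fits neither CR nor PR. That holds only on the mandatory reading. On the sensible one, CT-assessed subjects are PR and still count towards ORR. The gap for FDG-avid, PET-negative subjects does not depend on this bullet.

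**The waiver is not general.** A reader might infer that 1.4.6 dispenses with biopsy for all lymphoma subjects. It does not: a positive or unexamined baseline marrow that PET does not clear still needs one.

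**Section 11 is not a competing rule.** That section says "a repeat bone marrow biopsy or aspirate will be required for subjects who have a Complete Response (CR) by imaging and physical examination", and a reader might infer that an aspirate is offered for a criterion it can never meet. The sentence applies only where the response criteria make a sample necessary, as do the matching schedule footnotes. Section 11 and the monotherapy footnotes also serve CLL/SLL, where 2.2 excludes PET and 2.5.2 asks only for a marrow sample. No contradiction follows, and a core-biopsy-or-PET rule there would be wrong for CLL/SLL.

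**The source is a log.** This stands as a limit. The conflict is internal to one block of replacement wording, and the later log entries available show no change to these criteria, but those entries are incomplete and the current appendix was not available to check.

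**Conclusion.** The inconsistency is real and should be corrected. Section 1.5.1 contradicts itself and 1.4.6, and 1.5.2 lists an alternative route to PR as a mandatory condition.

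With the last PR bullet read as an alternative, there are two effects. Complete responders assessed by CT who have a negative baseline biopsy and no repeat are CR under 1.4.6 but PR under 1.5.1 and 1.5.2; only the CR rate moves. FDG-avid, PET-negative complete responders without a biopsy, with a positive or no baseline PET, have no category among CR, PR and SD; for them ORR moves as well. One such subject in an FL cohort of 20 can decide whether the lower-bound condition is met at the final count.

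This rests on the amendment-log wording still being current and on such subjects occurring; how many is unknown. The documents do not show that CR rates differ between sites or cohorts for this reason.

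**What to change.** First confirm the wording against the current Appendix 2. If it stands:

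1. In 1.5.1, reconcile the two marrow bullets with 1.4.6 so that one marrow criterion remains and applies only where 1.4.6 calls for marrow documentation.
2. In 1.5.2, take the persistent-marrow bullet out of the all-of list and state it as a separate route to PR, for a subject who meets the CR criteria except for marrow.
3. Check the PET bullets in 1.5.2 and 1.5.3 together with these changes, so that no complete responder is left without a category.

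Leave Section 11 and the schedule footnotes unchanged. The cost is wording only, with no biopsies beyond those 1.4.6 already requires. If responses have already been assigned under this text, list the subjects in imaging CR without an on-study core biopsy and review their categories under the reconciled rule.

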1.5.2 Partial Response

To satisfy criteria for PR, all of the following conditions must be attained:

- No evidence of new disease
- $A \ge 50\%$ decrease from baseline in the SPD of the index nodal and extranodal lesions
- No increase from the nadir in the size of non-index disease
- No increase from the nadir in the size of the liver or spleen and no new liver or spleen enlargement
- If PET performed:
 - Typically FDG-avid lymphoma: if no baseline PET scan or if the PET scan was positive before therapy, the on-treatment PET is positive in ≥ 1 previously involved site—i.e., score of 4 (uptake moderately > liver) or score of 5 (uptake markedly > liver) on the Deauville 5-point scale but with reduced uptake compared with baseline. If baseline PET was performed and was negative, there is no new PET evidence of disease.
 - Variably FDG-avid lymphoma/FDG-avidity unknown: if no pretreatment PET scan or if the pretreatment PET scan was negative for lymphoma, CT criteria should be used in assessing the tumor during treatment. If the PET scan was positive before therapy, the on-treatment PET is positive in ≥ 1 previously involved site.

Version 9, 18 Feb 2020

• Persistence of bone marrow involvement in a subject who meets other criteria for CR based on the disappearance of all nodal and extranodal masses

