1.2 Method of Assessment

Imaging-based evaluation will be used in this study as the primary basis of lymphoma assessment. CT scan is the preferred method for radiographic tumor assessment. Contrast-

^{*} CR (complete remission): all of the criteria have to be met, and patients have to lack disease related constitutional symptoms; PR (partial remission): at least 2 of the criteria of group A plus one of the criteria of group B have to be met; SD is absence of progressive disease (PD) and failure to achieve at least a PR; PD: at least one of the above criteria of group A or group B has to be met.

[†] Sum of the products of multiple lymph nodes (as evaluated by CT scans in clinical trials, or by physical examination in general practice).

[‡] These parameters are irrelevant for some response categories.

Version 9, 18 Feb 2020

enhanced scanning is preferred, but contrast material may be omitted in subjects for whom use of a contrast agent becomes medically contraindicated or if CT scanning is done in conjunction with PET. If available, PET scan data will be considered in response and progression assessment; however, PET scanning will not be a required component of assessment in this study. As necessary, bone marrow aspirate/biopsy (e.g., for confirmation of CR) or cytological/histological evaluation of lymph nodes, effusions, ascites, or other organ abnormalities) will be also be considered. Clinical palpation, chest x-ray, ultrasound, endoscopy, laparoscopy, radionuclide scan, or tumor markers will not be considered for response assessment. MRI scanning is not advised but may be used at the investigator's discretion in subjects for whom this becomes a necessary alternative to CT scanning.

For radiographic assessments, the same method of assessment and the same technique (e.g., scan type, scanner, subject position, dose of contrast, injection/scan interval) should be used to characterize each identified and reported lesion at baseline and during study treatment and follow-up. CT of the neck, chest, abdomen, and pelvis should be performed with cuts of ≤ 0.5 mm in slice thickness contiguously. If performed, whole-body FDG PET-CT scanning should be extended from the base of the skull to mid-thigh.

All relevant radiographic and clinical information required to make each tumor status assessment must be made available for source verification as requested by the study sponsor.

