1.5.3 Stable Disease

To satisfy criteria for SD, all of the following conditions must be attained:

- No evidence of new disease
- Neither sufficient tumor shrinkage from baseline to qualify for PR nor sufficient evidence of tumor growth to qualify for PD
- If PET-CT performed, the results show a score of 4 (uptake moderately > liver) or score of 5 (uptake markedly > liver) on the Deauville 5-point scale with no significant change in uptake compared with baseline.

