1.5.4 Progressive Disease

The occurrence of any of the following events indicates progressive disease (PD):

- Evidence of any new disease that was not present at baseline:
 - A new node that measures > 1.5 cm in any diameter
 - A new node that measures > 1.0 cm to ≤ 1.5 cm in the LD and > 1.0 cm in the LPD
 - Reappearance of an extranodal lesion that had resolved (i.e., had previously been assigned a PPD of 0 cm²)
 - o A new extranodal lesion of any size
 - New non-index disease (e.g., effusions, ascites, or other organ abnormalities) of any size unequivocally attributable to lymphoma (usually requires PET, biopsy, cytology, or other non-radiologic confirmation to confirm disease attributable to lymphoma). Note: Isolated new effusions, ascites, or bone lesions are not sufficient evidence alone of PD unless histologically confirmed. In patients with no prior history of pulmonary lymphoma, new lung nodules identified by CT are usually benign. Thus, a declaration of PD should not be made if this is the only manifestation of an apparently new lesion.
 - New FDG-avid foci consistent with lymphoma rather than another etiology (e.g., infection, inflammation). If there is uncertainty regarding the etiology of new lesions, biopsy or interval scan may be considered.
 - New or recurrent bone marrow involvement with lymphoma by PET-CT or by bone marrow biopsy if prior PET-CT or bone marrow biopsy performed as part of the study was negative for lymphoma.
- Evidence of worsening of nodal or extranodal index lesions:
 - Increase from the nadir by \geq 50% in the SPD of index lesions
 - Evidence of worsening of individual index lymph nodes or nodal masses:
 - Increase from the nadir by ≥ 50% in the PPD for any individual node if the node now has an LD of > 1.5 cm and there is an absolute change from the nadir of ≥ 0.5 cm in the LD or LPD and to an absolute dimension of ≥ 2.0 cm.

Version 9, 18 Feb 2020

- Increase from the nadir by ≥ 50% in the LD for any individual node if the node now has an LD of > 1.5 cm and there is an absolute change from the nadir of > 0.5 cm in the LD
- Increase from the nadir by ≥ 50% in the LPD for any individual node if the node now has an LPD of > 1.5 cm and there is an absolute change from the nadir of ≥ 0.5 cm in the LPD
- If a lesion had been classified as a small lymph node, there is an additional requirement that the lesion has an LD of > 1.0 cm and an LPD of > 1.0 cm
- Unequivocal increase in the size of non-index disease

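### The PR rule for FDG-avid lymphoma asks subjects with no baseline PET for a fall in uptake from baseline, so a CT partial response with a Deauville 4–5 PET at the same visit fits none of CR, PR, SD or PD

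*Combined protocol and SAP*

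**What the plan says.** All wording here comes from the amendment log appended to protocol Version 9. It is the replacement text for Appendix 2, not the struck-out text. The current Appendix 2 is not in the part reviewed.

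- **PR is an all-of list** (1.5.2): "To satisfy criteria for PR, all of the following conditions must be attained".
- **PET item, typically FDG-avid lymphoma** (1.5.2). One branch covers two groups: "if no baseline PET scan or if the PET scan was positive before therapy, the on-treatment PET is positive" in at least one previously involved site. For both groups it asks for a score of 4 or 5 "on the Deauville 5-point scale but with reduced uptake compared with baseline". A separate sentence deals with a negative baseline PET.
- **PET item, variably avid or unknown avidity** (1.5.2). With no pretreatment PET, or a negative one, "CT criteria should be used in assessing the tumor during treatment".
- **SD** (1.5.3): "Neither sufficient tumor shrinkage from baseline to qualify for PR nor sufficient evidence of tumor growth to qualify for PD". If PET-CT was done, SD also needs a score of 4 or 5 with no significant change from baseline uptake.
- **CR** (1.5.1). If PET was done, the score must be 1, 2 or 3.
- **NE.** Section 1.5 provides NE where information is inadequate to categorize response. The list in 1.5.5 names only absent, inadequate or missing images.
- **Use of PET** (1.2): "PET scanning will not be a required component of assessment in this study", but PET data are to be considered when available. Sections 8.1.5 and 11 allow either diagnostic CT or PET/CT at baseline in lymphoma.
- **Counting.** Section 14.3.1 counts NE as failure in the full analysis set. The Stage 2 rules in 14.1.2 count responders among evaluable subjects. Section 6.1.4 makes evaluability depend on assessments sufficient to determine response, and 6.13 lets non-evaluable subjects be replaced.

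**The concern.** The FDG-avid branch names subjects without a baseline PET and then sets them a condition that needs one. The neighbouring sub-bullet sends the same situation to CT, so this looks like a drafting slip rather than a choice.

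The criteria also give a reason to obtain a first PET in a good CT responder. Metabolic criteria take precedence when assessing CR (1.5), and PET can stand in for a marrow biopsy (1.4.6). If that scan scores 4 or 5, CR is not reached, and the PR that CT alone supports is no longer available at that visit under the written rule.

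The expansion cohorts are judged on counts of at most about 20 subjects, several of them on 6, so one reclassified responder can change a cohort's conclusion.

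**Working it through.** **1. Which category fits?** Take a typically FDG-avid lymphoma with a CT-only baseline. At one visit the SPD has fallen by at least 50%, there is no new disease, and a first PET scores 4 or 5.

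| Category | Met as written? | Reason |
|---|---|---|
| CR | No | Score must be 1–3 |
| PR | No | CT part met; fall in uptake from baseline cannot be assessed |
| SD | No | Shrinkage is sufficient for PR; PET item also needs baseline uptake |
| PD | No | No growth and no new disease |
| NE | Probably | Fits the general definition in 1.5; not named in 1.5.5 |

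Three neighbouring cases are not affected. A positive baseline PET with reduced uptake meets the PET item. A negative baseline PET needs only no new PET disease. An on-study score of 1–3 can lead to CR if the other items are met.

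**2. The plan's own boundary.** Section 14.1.2 gives 8/20 as the last follicular lymphoma monotherapy boundary, with one-sided alpha 0.05 and a lower bound of at least 20%.

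- Exact lower one-sided 95% bound = 5% quantile of Beta(x, n − x + 1).
- Exact p = P(X ≥ x) for X ~ Binomial(n, 0.20).
- For 8/20: bound 0.217, p = 0.032. The plan's figure reproduces.

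**3. One response fewer.**

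| Count | Handling of the lost subject | ORR | Lower bound | p against 20% |
|---|---|---|---|---|
| 8/20 | counted as PR | 0.400 | 0.217 | 0.032 |
| 7/20 | NE kept as failure | 0.350 | 0.177 | 0.087 |
| 7/19 | NE dropped as non-evaluable | 0.368 | 0.188 | 0.068 |

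Both alternatives miss the boundary. The p-values are single-look tails and make no allowance for continuous monitoring.

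For the rituximab combination, where the lower bound must be at least 39%, 12/20 gives 0.394. One fewer gives 0.347 at 11/20 or 0.368 at 11/19, and both miss.

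In a six-subject cohort, a single lost response turns 1/6 into 0/6. The one-sided 90% upper bound is then 1 − 0.1^(1/6) = 0.319, the plan's 32%, and an ORR of 35% would be declared excluded. If the subject is dropped, 0/5 gives 1 − 0.1^(1/5) = 0.369 and 35% is not excluded.

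**4. Sensitivity.** The documents give no frequency, so the lost share f of responders is an assumption. With a true ORR of 40%, 20 subjects and lost responses kept as failures, the chance of reaching 8/20 in a single look is P(X ≥ 8) at rate 0.40 × (1 − f):

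| f | Rate | P(≥ 8/20) |
|---|---|---|
| 0 | 0.40 | 0.584 |
| 5% | 0.38 | 0.511 |
| 10% | 0.36 | 0.436 |
| 20% | 0.32 | 0.292 |

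**The case against.** Several points on the other side are sound.

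- **Best overall response protects most responders.** Section 1.5 takes the best response from the start of treatment until progression. A reader might infer that a later PET erases a PR. It does not: a PR recorded at a CT-only visit stands. The loss needs a PET scored 4–5 at every visit where the subject would otherwise qualify.
- **The group is narrow.** A reader might infer that any CT partial responder with an on-study PET is lost. The unaffected cases above show otherwise. Section 1.2 also says the same method should be used throughout, and 8.1.5 expects combined PET/CT in most cases. This makes the gap less likely but does not close it.
- **Progression is a separate matter.** A reader might infer that any focus on a first PET could be called PD under "New FDG-avid foci consistent with lymphoma rather than another etiology". The parent bullet in 1.5.4 is limited to disease not present at baseline, which CT also documents, and biopsy or an interval scan is offered when etiology is uncertain. That reading is not supported.
- **The list is loosely drafted.** Its last item, persistent marrow involvement, cannot be a condition for every PR. One may therefore read the FDG-avid branch as meant to admit subjects without a baseline PET, comparing uptake only where possible. That may be the intention, but the text does not say so, and assessors could differ.
- **Non-evaluable subjects may leave the count.** This is correct under 6.1.4 and 6.13, so 7/20 is not the only outcome. However, 7/19 also misses, and a replacement need not respond.

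**Conclusion.** The contradiction in 1.5.2 is real and confined to one situation: typically FDG-avid lymphoma, no baseline PET, and an on-study PET scored 4–5 at a visit with a CT partial response. NE is the likely result, though 1.5.5 does not name it. That is a failure in the full analysis set and possibly an exclusion from the Stage 2 n/N counts.

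One such loss is decisive at the follicular lymphoma boundaries, but how many subjects are affected is unknown. A reader might infer a bias in ORR of known size; the documents do not support one. Nor is the direction fixed. A subject with stable disease on CT in the same position also misses SD, and if treated as non-evaluable would remove a non-responder from N.

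The conclusion assumes that this replacement wording still stands. No later change to it appears in the log as reviewed, but some pages are missing. The point is a should-fix, held with moderate confidence.

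**What to change.** First confirm the wording in the current Appendix 2. Then:

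1. In 1.5.2, remove the no-baseline-PET alternative from the typically FDG-avid sub-bullet, and state that without a baseline PET, PR is assigned by CT criteria, as the variably avid sub-bullet already provides.
2. In 1.5.3, apply the PET item only when a baseline PET exists.
3. Leave the PD bullet on new FDG-avid foci unchanged. Restricting it to subjects with a prior PET could ignore true progression detected by PET.

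The cost is two sentences and a re-derivation of response from data already collected, with no new scans. The Stage 3 text describes a data cutoff and database lock, so a change made after that point would be post hoc. In that case, write the rule before re-deriving, report the number of subjects affected, and show ORR under both the recorded and the re-derived responses.
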